## **1.2. The results of nonclinical and clinical studies relevant to this study.**

A detailed description of the results of preclinical and clinical trials of influenza tetravalent inactivated subunit vaccine Grippol® Quadri (NPO Petrovaks Farm, Russia) is presented in Investigator's Brochure.

### **Nonclinical studies**

*Antigenic activity (immunogenicity) of Grippol® Quadri [13].*

Strictly confidential. Proprietary Information.  
[name]

Antigen activity of Grippol® Quadri was assessed by the level of specific antibodies to hemagglutinin in serums of immunized mice. The level of antibodies was determined by hemagglutination inhibition test (HAIR) and by enzyme-linked immunosorbent assay (ELISA). The conducted studies have shown that antibodies to hemagglutinin of each strain of the vaccine are produced in mice in response to administration of Grippol® Quadri, as was shown in all the performed tests. The geometric mean antibody titers (GMAT) determined in animals after administration of Grippol® Quadri did not significantly differ from those for the trivalent vaccine Grippol® Plus. In one test, the level of antibodies after administration of quadrivalent vaccine was even higher than that for a similar dose of trivalent vaccine. GMAT obtained by HAIR for Grippol® Quadri were 1:113, 1:242, 1:86, 1:92 for strains A/H1N1/California/07/09, A/H3N2/Switzerland/9715293/13, B/Phuket/3073/13 and B/Brisbane/60/08 respectively. Equivalent values for Grippol Plus: 1:75, 1:80, 1:65. The B/Brisbane/60/08 strain was not included in the trivalent vaccine, so the level of antibodies to it was not measured. Thus, it can be concluded that the inclusion of additional five micrograms of hemagglutinin strain B/Brisbane/60/08 in the vaccine does not reduce the intensity of the immune response to other strains. In addition, the studied vaccines provided 100 % seroprotection of animals, i.e. GMAT to hemagglutinin of each strain was  $\geq 1:40$ .

It was shown that POx acts as an adjuvant in the composition of tetravalent vaccine, in particular, it enhances the production of antibodies to hemagglutinin. GMAT for polyoxide-free antigens was 1:87, 1:113, 1:80 for strains A/H1N1/California/07/09, A/H3N2/Switzerland/9715293/13, B/Phuket/3073/13 respectively. Equivalent values for Grippol® Plus: 1:123, 1:247, 1:104.

ELISA results support the data obtained by HAIR. Immunization of animals led to the production of antibodies to hemagglutinin of both IgG1 and IgG2a subclasses. It is known that an increase in the level of IgG1 antibodies reflects activation of humoral, and an increase in IgG2a — cellular immunity.

In the second test, the amount of cytokine IL-4 in supernatants of mouse splenocyte pre-stimulated with a mixture of hemagglutinins was determined. According to the obtained results, it can be concluded that the humoral immunity is activated in mice that received Grippol® Quadri. Index of IL-4 stimulation was 3.9. Same parameter for trivalent vaccine was 4.3.

During the nonclinical efficacy studies of the Grippol® Quadri influenza vaccine containing hemagglutinin and neuraminidase of four influenza virus strains, the antigenic activity of the novel product was investigated. In the three studies with laboratory mice it was shown that the Grippol® Quadri vaccine represented high antigenic activity comparable or even exceeding that of the trivalent vaccine. The presence of the 4th strain B/Brisbane/60/08 Victorian line influenza virus antigens in Grippol® Quadri did not reduce immune activity of other vaccine antigens.

---

Strictly confidential. Proprietary Information.  
[name]

It should be noted that even considering the 4th strain, the total amount of hemagglutinin in one dose of Grippol® Quadri was 20 µg/dose, which is almost twice less than that usually included in the trivalent inactivated influenza vaccines without adjuvant (45 µg/dose). Grippol® Quadri vaccine includes POx making the antigen dose of 20 µg sufficient and effective. The amount of POx in Grippol® Quadri is 500 µg. This amount of POx in the trivalent polymer-subunit vaccines Grippol® plus and Grippol® with a total HA content of 15–21 µg has proven its efficacy and safety. The studies showed that the "antigen-adjuvant"-related antibody response for each product significantly exceeded the antigen-mediated immune response without adjuvant.

#### *Assessment of administration safety*

##### *Acute toxicity of Grippol® Quadri vaccine [14]*

The acute toxicity of the Grippol® Quadri vaccine was evaluated in 40 male and female white mice (10 mice per group) when administered subcutaneously at a single dose of 1,600 and 3,200 µg HA/kg that, respectively, 2,000 and 4,000 times exceeds the maximum permitted dose in human (based on a child weighing 10 kg, i.e. about 0.8 µg/kg). In the control groups, the animals were administered normal saline solution and vehicle (vaccine solvent) — phosphate saline buffer solution.

The criteria for assessment of toxicity were: indicators of body weight change, signs of impaired health in animals during a clinical examination, indicators of changes in peripheral blood, a macro- and microscopic picture of cavities and internal organs.

During the study, no animal death, as well as clinical signs of toxicity following a single-dose subcutaneous administration of the Grippol® Quadri vaccine to the male and female mice at the doses of 1,600 µg HA/kg and 3,200 µg HA/kg were observed. The necropsy carried out on animals 7 days after the administration show no macroscopic changes in the organs or tissues, their location relative to each other, size, shape, color, or consistency; no pathological changes in the structure of the walls, mucous membranes, intracranial, abdominal, or pleural cavities. As a result of the analysis of histological specimens, a moderate reaction of the organs of the immune system (thymus, spleen, regional lymph node) was revealed. Thymocyte emigration, delymphatization of thymus-dependent areas in the white pulp of the spleen and a regional lymph node, an increase in the number of plasma cells in the lymph node medulla were observed. These structural transformations of the lymphoid organs are the hallmark of the immune reactions occurring in response to vaccination with significant doses. In other organs and tissues, as well as at the administration site no changes were detected.

##### *Repeat dose toxicity [15]*

Study products were administered to male and female Wistar rats intramuscularly once a week for 6 weeks at doses of 20 and 100 HA µg/kg. Animals in control group received in a similar way an equivalent amount of saline and the vehicle (vaccine diluent) — phosphate saline buffer.

Strictly confidential. Proprietary Information.  
[name]

During the observation period, test animals did not show decreased body weight gain, clinically significant abnormalities in food and water intake or functional parameters of central nervous system and cardiovascular system, as well as changes in the peripheral blood cell counts and serum biochemical values.

Urine biochemical analysis in female rats following 6 intramuscular injections of the Grippol® Quadri vaccine at a maximum dose of 100 HA  $\mu$ g/kg revealed a significant decrease of 24-hour excretion of chlorides and urea along with a decline in the daily urine output. The blood serum urea and chlorides levels were within the normal ranges; therefore, there were no reasons to suggest any serious tubular reabsorption impairment.

Histological findings in the liver and kidneys demonstrated moderate vascular reactions and changes in convoluted tubules epithelium; in other studied internal organs and tissues, when compared to the control, any significant pathological abnormalities have not been revealed.

Therefroe, the studies showed that there were no significant deviations in the health status of study animals following the immunization with Grippol® Quadri vaccine, manufactured by NPO Petrovax Pharm, LLC, containing locally produced influenza virus antigens at a dose of 20  $\mu$ g per 0.5 ml, which indicates the safety of the study drug.

#### *Assessment of local effect.*

The assessment of local effect was included in the acute and chronic toxicity studies in mice and rats based on the clinical examination data and the results of the histological examination of the injection site (muscle and surrounding tissues).

Macroscopic examination of the injection site after a single subcutaneous injection of Grippol® Quadri to mice at doses of 1,600 and 3,200 HA  $\mu$ g/kg and after a course of intramuscular administration to the Wistar rats showed no significant differences in the skin, subcutaneous tissue, and adjacent tissues condition, following the administration of the investigational product and physiological saline solution as a control.

Histological examination of the injection site after 6 intramuscular administrations of the vaccine to male and female rats at doses of 20 and 100 HA  $\mu$ g/kg has shown the presence of small haematomas in isolated cases in the control and test groups of males and females. This non-specific reaction is a response to the mechanical impact, it is not the result of the local irritant effect.

#### *Assessment of immunologic safety [16].*

Immunological safety assessment of the Grippol® Quadri vaccine (in total, 20  $\mu$ g of HAs of the three strains per dose plus 500  $\mu$ g of Polyoxidonium) consisted of nonclinical investigation of the immunoreactivity changes in the experimental animals (mice, guinea pigs) associated with the specific immune response to the immunization. The vaccines containing similar hemagglutinin and POx levels were used as comparators: commercially available vaccine Grippol® Plus (a total of 15  $\mu$ g HA of the 3 strains per dose and 500  $\mu$ g of POx) and vaccine Grippol® (a total of 21  $\mu$ g HA of the 3 strains per dose and 500  $\mu$ g of POx).

---

Strictly confidential. Proprietary Information.  
[name]

The ability of vaccines to influence the humoral, cellular, and macrophage parts of the immune response at different times after vaccination was evaluated in mice. Immunological reactivity of mice after the study vaccine administration was estimated according to the accumulation of antibody-producing cells in mice spleen after their immunization with sheep red blood cells (a model of humoral immune response), the development of delayed-type hypersensitivity during the plantar test (a model of cell-mediated immune response). Activity of phagocytes was estimated according to the respiratory burst process in the spontaneous and induced chemical luminescence setting. Investigators also studied the possibility of the polyclonal effect of the study vaccines by the ability to nonspecific stimulation of antibody-forming cells to various test antigens.

The findings of the animal studies performed have demonstrated that the specific immune response to the vaccine does not preclude both acute and long-term post-immunization normal immune reaction to the antigens heterologous to those presented in vaccines. The stimulating effect of the Grippol® Quadri vaccine on the humoral immune response to the heterologous test antigen (the ram erythrocytes) has been proven. It was shown that immunoadjuvant action is not associated with polyclonal properties, which is the immune system safety indicator. The investigation of the study vaccine effect on the multi-local phagocytic activity and the cellular immune response did not reveal effects specific for the possible immunotoxic effect of immunization.

The Grippol® Quadri vaccine allergenic properties [17] were assessed in animals (guinea pigs and mice) using the immediate (ITH) and delayed type (DTH) response testing with multiple administrations of the product.

Like the Grippol® vaccine, the Grippol® Quadri vaccine was not found to have any local irritative effect (at a dose of 1/10 BH) and did not cause the delayed-type allergic reaction following multiple administration of the maximum possible testing amount (1/5 and 1/10 of BH) to mice.

During evaluation of the possibility to sensitize guinea pigs (the most sensitive animal species) in the immediate-type hypersensitivity reaction, there were no signs of sensitization revealed with repeated Grippol® Quadri injections, suggesting an extremely low probability of allergic reactions associated with the vaccine administration to humans.

Summarizing the results of the conducted research, we can conclude that the domestic tetravalent vaccine for the prevention of influenza Grippol® Plus containing 2 strains of influenza virus types A and B in nonclinical studies has shown high efficiency and safety. It can be expected that the use of Grippol® Quadri vaccine will provide better protection to the population against influenza.

### **Clinical studies [20]**

Phase I safety and tolerability study of quadrivalent inactivated subunit influenza vaccine Grippol® Quadri was conducted in healthy volunteers [20].

---

Strictly confidential. Proprietary Information.  
[name]

The study included 3 groups of 30 subjects, overall 90 subjects. Subjects from group 1 (30 volunteers) received a single 0.5 ml dose of Grippol® Quadri; Group 2 (30 volunteers) received a single 0.5 ml dose of the reference vaccine Grippol Plus; Group 3 (30 volunteers) received a single 0.5 ml dose of placebo (saline solution).

Over the study period, there was a minimum of 1 AE in the Grippol® Quadri group, Grippol® Plus group, and Placebo group in 36.7 %, 30.0 %, and 20.0 % of the subjects respectively. The majority of all registered AEs were classified as post-immunization reactions (reactogenicity symptoms — local and system reactions) and were considered by the Investigator as related to the study product (strength of relation: "definite", "probable", and "possible").

During the evaluation of the reactogenicity in the Grippol® Quadri group, the local reactions were detected in 33.3 % of the subjects, in the group Grippol® Plus, there were 23.3 % of the subjects, and in the Placebo group, 13.3 % of the subjects. Among the local reactions, there were observed pain at the injection site, erythema, swelling and induration, and itching at the injection site. Pain at the injection site was the most common local reaction in all three study groups. No additional medical intervention was needed for the local reactions in the subjects. Local reactions were mild to non-identified by severity. During the comparative evaluation, there was no evidence of the statistically significant difference between the proportion of mild, moderate, and severe local reactions in the Grippol® Quadri group, Grippol® Plus group, and Placebo group ( $p = 1.00$  and  $p = 1.00$  respectively).

Only the subjects without any intercurrent conditions within the first five days after immunization were included in the system reactions analysis: in total 29 of the 30 subjects from the group Grippol® Quadri, 28 of 30 subjects from the group Grippol® Plus, and 29 subjects from the Placebo group. During the evaluation of the reactogenicity, the general reactions were detected in the group Grippol® Quadri in 20.7 % of the subjects, in the group Grippol® Plus in 3.6 % of the subjects, and in the Placebo group in 10.3 % of the subjects. Among the general reactions recorded during the study, there were the following: rise in body temperature above 37 °C, malaise, headache, nausea, myalgia / arthralgia. The most common general reaction in the group Grippol® Quadri was the development of headache — in 13.8 % of the subjects, whereas in the group of Grippol® Plus and in the Placebo group headache was observed only in 3.6 % and 3.4 % of the subjects respectively. The rise in body temperature above 37 °C was recorded in 6.9 % of subjects in the group Grippol® Quadri (within subfebrile with a maximum registered value of 37.2 °C), and also in 6.9 % of subjects in the Placebo group (within subfebrile with a maximum registered value of 37.5 °C). All the occurred systemic reactions were regarded as mild. During the comparative evaluation, there was no evidence of the statistically significant difference between the proportion of mild, moderate, and severe local reactions in the Grippol® Quadri group, Grippol® Plus group, and Placebo group ( $p = 0.102$  and  $p = 0.470$  respectively).

Strictly confidential. Proprietary Information.  
[name]

The results of the laboratory tests and neurological status assessment did not reveal any significant changes over the study period. In addition, the results of the analysis of all vital signs excluding body temperature (clinically significant subfebrile increase of body temperature in 2 subjects during the vital signs assessment) did not reveal any considerable changes over the study period. Clinically significant body temperature abnormalities were recorded within the frames of the registered AEs. The results of the physical examination evaluations, except for the data on the condition of the respiratory system and mucous membranes (in 1 subject diagnosed with respiratory tract infection, nasopharyngitis), were within the normal range. Clinically significant abnormalities were registered as AEs.

### **1.3. Known and potential risks and benefits for study subjects**

Known and potential risks of the study vaccine and comparison vaccine are described below. When determining the causal relationship of the adverse events that occur during this study, the investigator must take into account all the information described below, as well as information from the current version of the draft of the instruction for medical use and information from the latest version of the investigator's brochure on the study drug.

#### **Potential risks of using the study drug:**

Inactivated influenza vaccines are highly purified drugs and are well tolerated. Based on the published literature, the results of non-clinical studies and the phase I clinical study, it is expected that the safety profile of quadrivalent vaccine under investigation will be the same as the profile of trivalent comparison vaccines. Adverse events and their frequency are listed below.

*Common* ( $> 1/100, < 1/10$ ). Local reactions in the form of sore, redness, swelling, and itching in the administration site. Systemic reactions: malaise, fatigue, subfebrile temperature.

*Infrequent* ( $> 1/1,000, < 1/100$ ). Systemic reactions such as mild runny nose, sore throat, headache, temperature above subfebrile.

Usually the above mentioned reactions pass off in 1–2 days.

*Rare* ( $> 1/10,000, < 1/1,000$ ). Allergic reactions including the immediate ones.

*Very rare* ( $< 1/10,000$ ).

- nervous system disorders: neuralgia, paresthesia, neurological disorders;
- locomotor system disorders: myalgia.

53 adverse events in 26 volunteers have been recorded during phase I clinical study. All the AEs were of a mild to moderate severity. None of the adverse events was a reason for the subject's withdrawal from the study. Among the AEs, there were no serious adverse events (SAE). Characteristics of adverse events (system organ classes and association to the study drug) are presented in Table 1.

Strictly confidential. Proprietary Information.  
[name]

**Table 1. Number of Volunteers with Adverse Events Associated With the Study Drug (Degree of Association: "definite", "probable", and "possible") distributed according to the System organ class and the preferred term (MedDRA)**

System Organ Class: preferred Term, n* (%)	Degree of Association With the Study Drug	Group Grippol® Quadry N = 30	Group Grippol® Plus N = 30	Group Placebo N = 30
Total number of subjects with adverse events (any AEs)	Definite	1 (3.3 %)	1 (3.3 %)	0 (0.0 %)
	Likely	9 (30.0 %)	5 (16.7 %)	4 (13.3 %)
	Possible	1 (3.3 %)	1 (3.3 %)	1 (3.3 %)
General disorders and administration site conditions:	Definite	1 (3.3 %)	1 (3.3 %)	0 (0.0 %)
	Likely	9 (30.0 %)	5 (16.7 %)	4 (13.3 %)
	Possible	0 (0.0 %)	1 (3.3 %)	0 (0.0 %)
Erythema at the injection site	Likely	1 (3.3 %)	1 (3.3 %)	1 (3.3 %)
Pain at the injection site	Definite	1 (3.3 %)	1 (3.3 %)	0
	Likely	9 (30.0 %)	4 (13.3 %)	4 (13.3 %)
	Possible	0	1 (3.3 %)	0
Itching at the injection site	Likely	1 (3.3 %)	1 (3.3 %)	0
Swelling at the injection site	Likely	0	0	1 (3.3 %)
	Possible	2 (6.7 %)	0	1 (3.3 %)
Laboratory and instrumental data:	Possible	3 (10.0 %)	0	2 (6.7 %)
Increased body temperature	Possible	3 (10.0 %)	0	2 (6.7 %)
Skeletal muscle and connective tissue disorders:	Possible	0	0	1 (3.3 %)
Arthralgia	Possible	0	0	1 (3.3 %)
Myalgia	Possible	0	0	1 (3.3 %)
Nervous system disorders:	Likely	2 (6.7 %)	0	0
	Possible	3 (10.0 %)	1 (3.3 %)	1 (3.3 %)
Headache	Likely	2 (6.7 %)	0	0
	Possible	3 (10.0 %)	1 (3.3 %)	1 (3.3 %)
Drowsiness	Likely	1 (3.3 %)	0	0

\* — number of subjects with adverse events

**The expected benefits from the use of the study drug and the comparator drug:**

For a long time, trivalent influenza vaccines have been successfully used on the territory of the Russian Federation and around the world as an efficient and safe measure for prevention of influenza. The development of a quadrivalent vaccine containing strains of two lines of influenza B viruses will provide for a more reliable protection of the population, thus, increasing the immunization efficiency. Several trivalent vaccines (Fluarix Tetra, FluQuadri, Afluria, etc.) produced in Europe and the USA have already been successfully used in the world. In the Russian Federation, such drugs are currently not available.

---

Strictly confidential. Proprietary Information.  
[name]

Quadrivalent vaccine induces high-level specific anti-influenza immunity formation. Post-vaccination protective effect usually comes in 8–14 days, and the immunity retains up to 12 months, including elderly people. Protective anti-influenza antibody titers are detectable among 75–95 % of the vaccinated people of different age.

Development of the first Russian quadrivalent vaccine will help improve the effectiveness of vaccination and significantly improve the cost-effectiveness of preventive immunization.

#### **1.4. Description and justification of the mode of administration, dosage, dosage regimen, and course of treatment**

As there are no quadrivalent inactivated influenza vaccines approved on the territory of the Russian Federation and also due to similarity of antigens used for manufacture of quadrivalent and trivalent vaccines, the use of trivalent inactivated polymer-subunit influenza vaccine Grippol® Plus as a reference product is considered to be justified.

Therefore, to get comparative data for all the four antigens of the quadrivalent vaccine, the study will use two trivalent reference vaccines with different type B influenza virus antigens.

The study will be conducted in three groups (A, B, C):

Group A: Grippol® Quadri, quadrivalent inactivated subunit influenza vaccine, suspension for intramuscular and subcutaneous administration.

Group B: Grippol® Plus, trivalent inactivated polymer-subunit influenza vaccine, based on type B influenza virus of Yamagata lineage, suspension for intramuscular and subcutaneous injections.

Group C: Grippol® Plus, trivalent inactivated polymer-subunit influenza vaccine, based on type B influenza virus of Victoria lineage, suspension for intramuscular and subcutaneous injections.

**Dosing:** All the vaccines used in the study are administered as a single intramuscular injection of 0.5 ml (1 dose) into the upper third of the outer surface of the shoulder (the deltoid muscle).

The recommended dose and mode of administration of vaccines correspond to those described in the instructions for medical use of comparator vaccines. The duration of the observation of volunteers to identify adverse events after a single vaccination will be 6 months. A detailed description of the vaccination procedure by study vaccines is presented in Section 5.1.

Strictly confidential. Proprietary Information.  
[name]

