***Telephone calls (Visits 8–11):***

Telephone calls are made on Day 43±5 (Visit 8), Day 64±5 (Visit 9), Day 122±5 (Visit 10), Day 180±5 (Visit 11) and included the following procedures:

- Interviewing on ARI symptoms within the period.
- Assessment for exclusion criteria.
- Recording of concomitant therapy.
- Recording adverse events and intercurrent disorders.

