### 7.2. Methods and terms of evaluation, recording, and analysis of safety parameters

Evaluation of local and systemic reactions, as well as AEs, will be performed from the moment of immunization and within 6 months of follow-up. Recording of safety parameters will include the following procedures:

- clinical interview of a study subject;
- recording of thermometry results and complaints of a study subject related to his/her medical condition in a volunteer's diary;
- physical examination (including neurological status);
- vital signs;
- laboratory investigations
  - complete blood count and blood chemistry;
  - urinalysis;
  - evaluation of immunological parameters: serum immunoglobulin content (ELISA: IgE);
- quantitative assessment and nature (severity and duration) of local and systemic reactions to vaccine administration (reactogenicity);
- recording of AEs and SAEs associated with the study vaccines;
- recording of immediate type AEs, emerging within one hour after immunization;
- evaluation of incidence and nature of intercurrent disorders.

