### **7.3. Reporting requirements, procedures for recording and reporting of adverse events and intercurrent diseases**

An **adverse event (AE)** is any adverse change of a study subject's condition upon administration of the medicinal product, irrespective of the causal relationship with its administration. AEs include all adverse and unintended changes (e.g., deviation of a laboratory parameter), symptoms or diseases, where the time of occurrence does not rule out the causal relationship with administration of the medicinal product (manifestations absent in a subject prior to enrollment and developing during participation in a study, or manifestations observed in a volunteer prior to enrollment, the severity of which increases during the study upon administration of study products), irrespective of relationship with administration of the medicinal product.

An **adverse drug reaction (ADR)**, with regard to pre-approval clinical use of a new medicinal product, includes all negative reactions associated with administration of any dose of the medicinal product. The term "associated with administration of the medicinal product" means at least a minimum possibility of presence of a causal relationship between the medicinal product and the adverse event, i.e. correlation cannot be excluded. For registered medicinal products, the term "adverse drug reactions" means all negative reactions associated with administration of the medicinal product in standard doses used for prevention, diagnostics, or treatment of diseases, as well as for modification of physiological functions.

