#### **7.3.1. Recording of adverse events**

Procedures for recording the AEs are described in Section 7.2. AEs are recorded in the source medical documentation of a study subject, as well as in the respective sections of the CRF. Adverse events are recorded from the moment of administration of the first dose of the study product till the Study end visit.

The following information should be specified during recording of AEs:

- Nature of AEs (preferably with indication of the diagnosis, rather than the list of symptoms).
- Time of AE onset (*day, month, year, hour, minute*, where possible).
- Time of AE resolution (*day, month, year, hour, minute*, where possible).
- Severity of AE (*mild, moderate, severe*).

---

Strictly confidential. Proprietary Information.  
[name]

- Association with the study drug administration (*doubtful, possible, probable, definite*);
- Incidence of AEs (*single, intermittent*);
- Measures taken with regard to AE (*none, change of the study drugs dosing regimen, suspension of the study drugs administration, withdrawal of the study drugs, concomitant therapy*);
- Compliance of AE with SAE criteria (see Section 7.3.2; *yes, no*).
- Outcome of AE (*resolved without residual complications; resolved with residual complications; observed during the Study end visit; death of a study subject; lost to follow-up; stabilization of AE and its consequences*).

The investigator should try to establish the diagnosis based on the signs, symptoms, and other clinical information. If a diagnosis is determined, then the diagnosis itself should be recorded as an AE. If the diagnosis is unknown, then each complaint and symptom must be recorded as a separate AE.

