#### *Safety analysis*

The safety analysis will be conducted by descriptive methods in the safety population. Adverse events will be coded using MedDRA. The number (percentage) of participants with AEs and the number of AEs will be presented in tables by system organ class and preferred term, as well as by the study therapy and severity.

---

Strictly confidential. Proprietary Information.  
[name]

With that, within a system organ class and preferred term, each subject will be considered once with regard to study therapy and maximum severity. The number (percentage) of volunteers with local and general reactions to vaccination will be presented taking into account severity and duration.

Laboratory findings and their changes after vaccination compared to the baseline and “shift tables” relative to normal values will be tabulated by therapeutic groups and by assessment points.

The results of the assessment of vital functions will be tabulated by therapeutic groups for each assessment point together with changes from the last available measurement prior to vaccination.

The results of physical examination will be presented descriptively by therapeutic groups and by assessment points.

Immunological parameters evaluation results: serum immunoglobulin content (ELISA: IgE) and their changes after vaccination compared to baseline values will be tabulated by therapeutic groups.

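### AE tables run from vaccination to Day 180 with no split by onset and no rule for influenza/ARI endpoint cases, which costs the safety comparison some resolution

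*Combined protocol and SAP*

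**What the plan says.** **Period.** Section 1.4 sets six months of AE observation after one injection ("The duration of the observation of volunteers to identify adverse events after a single vaccination will be 6 months"). Section 7.2 agrees: "Evaluation of local and systemic reactions, as well as AEs, will be performed from the moment of immunization and within 6 months of follow-up". So does Section 7.3.1: "Adverse events are recorded from the moment of administration of the first dose of the study product till the Study end visit".

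**Collection.** Section 3.2 and Table 2 schedule clinic visits on Days 1–5 and at Visit 7 (Day 22±1). Section 7.2 has subjects keep a twice-daily temperature and complaints diary until Visit 7. After that there are four telephone calls, on Days 43, 64, 122 and 180 (each ±5). Each call includes both "Interviewing on ARI symptoms within the period" and "Recording adverse events and intercurrent disorders". Visit 7 also includes the ARI interview.

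**Definition.** Section 7.3 defines an AE as "any adverse change of a study subject's condition upon administration of the medicinal product, irrespective of the causal relationship with its administration". Section 7.3.1 adds: "If a diagnosis is determined, then the diagnosis itself should be recorded as an AE". Without a diagnosis, each symptom is a separate AE.

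**Tabulation.** Section 8.1, Safety analysis, says: "The number (percentage) of participants with AEs and the number of AEs will be presented in tables by system organ class and preferred term". Within a class and term each subject counts once, at maximum severity. No onset window is named. The same subsection does split laboratory, vital-sign and physical-examination results by assessment point. Local and general reactions are tabulated separately from AEs.

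**The concern.** Comparative safety is one of the study goals in Section 2. Effects of a single injection are expected soon after it, but the AE table covers about 180 days. Most of that time is background illness, collected by a different and less intensive method than in the first three weeks. Four features of the plan blur the early comparison:

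- The any-AE row mixes early events with whatever happens over the next five months.
- Symptoms in the influenza/ARI case definition of Section 6.2 (fever, headache, myalgia, cough) are also on the list of systemic reactions in Section 7.2. When they are recorded as symptoms, their preferred terms cannot be separated without onset time.
- Counting once at maximum severity lets a late illness overwrite an early event. A mild headache on Day 8 and a moderate one in month 5 appear as one moderate headache.
- AEs outside the reaction lists, and AEs starting between Day 6 and Visit 7, have no AE table except the six-month one.

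The documents also do not say whether influenza/ARI cases, which are efficacy outcomes, enter the AE tables. Different programmers could reasonably handle them differently.

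**Working it through.** **No plan figure to reproduce.** The documents give no size, power or precision for AEs. Their only design calculation (193 per group) concerns seroconversion.

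**Step 1: share of the window.** Five days of 180 is 5/180 = 2.8 %. Day 22 is 22/180 = 12.2 %. The telephone phase covers the remaining 180 − 22 = 158 days.

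**Step 2: how far an early difference in the any-AE row shrinks.** Inputs:

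- Early any-AE risk p: 36.7 % for Quadri and 30.0 % for Plus, from Phase I (Section 1.1; 30 subjects per group). Treating these as early-window rates is an assumption, because the documents do not state the length of Phase I follow-up.
- Background risk b of an AE from later illness: not in the documents. Assumed range 20–60 %, equal in all groups and independent of early AEs.
- Group sizes: 204 in A and 2 × 204 = 408 in pooled B and C (Sections 8.1 and 8.2).

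Six-month risk P = 1 − (1 − p)(1 − b), so the difference is (p_A − p_BC)(1 − b).

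The 95 % half-width is 1.96 × √[P_A(1 − P_A)/204 + P_BC(1 − P_BC)/408].

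| b | Group A | B + C | Difference (points) | Ratio | Half-width (points) |
|---|---|---|---|---|---|
| 0 | 36.7 % | 30.0 % | 6.7 | 1.22 | ±8.0 |
| 20 % | 49.4 % | 44.0 % | 5.4 | 1.12 | ±8.4 |
| 40 % | 62.0 % | 58.0 % | 4.0 | 1.07 | ±8.2 |
| 60 % | 74.7 % | 72.0 % | 2.7 | 1.04 | ±7.4 |

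Example for b = 20 %: 1 − 0.633 × 0.80 = 0.494 and 1 − 0.70 × 0.80 = 0.440, a difference of 5.4 points. The half-width barely changes while the difference falls. Even with no background, 6.7 ± 8.0 points includes zero, so windowing sharpens this row but would not settle it.

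**Step 3: what is not diluted.** The reactogenicity part of Section 7.2 has reactions assessed before vaccination, at 2 hours and daily for five days. I take the reaction table in Section 8.1 to follow that schedule, although Section 8.1 does not repeat it. Systemic reactions are assessed only in subjects without intercurrent disease, including ARI. With the Phase I general-reaction rates (20.7 % v 3.6 %, Section 1.2), the difference at this trial's sizes stays at 17.1 ± 5.8 points whatever the later illness rate.

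**Step 4: do influenza/ARI cases enter the AE tables?** The definition in Section 7.3 covers diseases irrespective of cause, diagnoses are recorded as AEs, and the calls collect ARI symptoms and AEs together. In Phase I (Section 1.2) a respiratory infection found on examination was registered as an AE. Entry into the AE tables is therefore the natural reading, but no section states it.

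**The case against.** A reader might infer that the AE comparison between vaccines is swamped by background illness, or that a significant safety signal would be missed. The case against that is strong, and most of it stands.

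- **The main early signal is protected.** Section 1.2 says most Phase I AEs were post-immunization reactions. Of the related terms in Table 1 (Section 1.3), all except drowsiness (one of 30 Quadri subjects) are on the reaction lists in Section 7.2. This stands.
- **Other separations exist.** AEs within one hour are a separate parameter, causality is graded, and a diagnosed ARI sits under its own term, leaving injection-site terms largely untouched. This stands. However, Section 8.1 does not clearly commit to a table of related AEs: its reference to study therapy could mean vaccine group or relationship to vaccine.
- **No AE test is planned.** The safety analysis is descriptive, so a power loss would describe an analysis that is not in the plan. This stands.
- **ARI may not be counted as an AE.** Section 7.3 goes on to refer to diseases whose timing does not rule out a causal link. The protocol also names intercurrent disorders separately and classes ARI among them. This shows that the rule is unclear. It does not supply an exclusion.
- **Section 8.1 opens by promising safety descriptives by time point.** That would permit an onset split, but the AE paragraph does not adopt one, while the laboratory, vital-sign and examination paragraphs do. Abnormalities of those three kinds are visible by visit in any case.
- **Six months of follow-up is not a fault.** Agreed; the point concerns tabulation only.

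A reader might also argue that better influenza protection from the quadrivalent vaccine would offset an early AE excess. All arms receive active vaccine, each comparator lacks one B lineage, and the documents give nothing from which to size such an effect. The calculation above assumes equal background and does not show it.

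**Conclusion.** The point holds in a limited form. Section 8.1 commits to one six-month AE tabulation across two different collection methods and gives no rule for influenza/ARI endpoint cases. The loss is confined to the any-AE row, the terms shared with ARI symptoms, maximum severity within a term, and AEs that are unlisted or start between Day 6 and Visit 7.

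Its size cannot be fixed from the documents. With Phase I any-AE rates as the starting point and an assumed equal, independent background of 20–60 %, a 6.7-point difference becomes 5.4–2.7 points. Those Phase I rates come from 30 subjects per group, so the figures illustrate the effect and do not forecast it. The documents do not support saying that the comparison is swamped, that every ARI case is certain to be counted as an AE, or that a planned test loses power.

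**What to change.** In Section 8.1, present the AE tables (class and preferred term, severity) three ways: onset from vaccination to Visit 7, onset after Visit 7 to Day 180, and overall. Apply the once-per-subject, maximum-severity rule within each window. Name a fixed cut-off day for anyone who misses Visit 7. Show AEs that are influenza/ARI endpoint cases on their own line, so that safety and efficacy events can be told apart. Keep SAEs over the full six months.

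No new data are needed, because Section 7.3.1 already requires the time of onset for each AE. The cost is a short wording change in Section 8.1 and one extra set of tables to produce and read.
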